^e Interactive Response Technology (IRT) will be used to allocate a 10 day supply of study drug at Visit 2 (or at the conclusion of Visit 1 after all eligibility criteria are confirmed to be met to allow time to prepare the study drug prior to day of randomization (first administration of study drug) and, if applicable per an individual patient's treatment duration, at Visit 12 and Visit 22.

^f If the patient discontinues treatment and is not discharged prior to Day 29, collect ventilation and oxygen parameters daily up to Day 29, respiratory rate, FiO₂, SpO₂, if applicable, at Day 29, and WHO Clinical Progression Scale score at Day 29. If patient is on oxygen therapy at discharge, collect end date of that oxygen therapy when available during the Follow-up visit telephone call(s).

^g ECG should be performed 0.5-4 hours after drug administration.

^h SARS-CoV-2 PCR test to be performed as visit procedure and an approved SARS-CoV-2 point-of-care test may be used to evaluate inclusion criterion 2, refer to [Section 3.3.2](#).

ⁱ Dosing should be stopped the day prior to EOT. However, if it is uncertain whether a patient is fit for discharge, and the patient has not yet completed the allowed treatment duration of 28 days, administer study drug and perform all study procedures per the planned treatment period visit. If later that day the PI makes the decision that patient will discharge, perform any additional EOT visit procedures, if applicable, per [Flow Chart](#) and record visit in the eCRF as EOT visit.

TABLE OF CONTENTS

| | |
|---|-----------|
| TITLE PAGE | 1 |
| CLINICAL TRIAL PROTOCOL SYNOPSIS | 2 |
| FLOW CHART | 4 |
| TABLE OF CONTENTS | 6 |
| ABBREVIATIONS | 9 |
| 1. INTRODUCTION..... | 12 |
| 1.1 MEDICAL BACKGROUND | 12 |
| 1.2 DRUG PROFILE | 13 |
| 1.3 RATIONALE FOR PERFORMING THE TRIAL | 15 |
| 1.4 BENEFIT - RISK ASSESSMENT..... | 16 |
| 1.4.1 Benefits | 16 |
| 1.4.2 Risks | 16 |
| 1.4.3 Discussion..... | 17 |
| 2. TRIAL OBJECTIVES AND ENDPOINTS..... | 18 |
| 2.1 MAIN OBJECTIVES, PRIMARY AND SECONDARY ENDPOINTS..... | 18 |
| 2.1.1 Main objectives..... | 18 |
| 2.1.2 Primary endpoint(s)..... | 18 |
| 2.1.3 Secondary endpoints | 18 |
| [REDACTED] | |
| 3. DESCRIPTION OF DESIGN AND TRIAL POPULATION..... | 20 |
| 3.1 OVERALL TRIAL DESIGN..... | 20 |
| 3.2 DISCUSSION OF TRIAL DESIGN, INCLUDING THE CHOICE OF CONTROL GROUP(S)..... | 20 |
| 3.3 SELECTION OF TRIAL POPULATION | 21 |
| 3.3.1 Main diagnosis for trial entry | 22 |

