3.3.3 Exclusion criteria

1. Alanine aminotransferase (ALT)/aspartate aminotransferase (AST) $> 5 \times$ the upper limit of normal (ULN).
2. Known active infection with HIV or hepatitis B or C.
3. Pulmonary oedema/respiratory failure due to cardiogenic insult.
4. Long-term oxygen therapy prior to current hospitalisation.
5. A confirmed baseline prolongation of QTc interval to greater than 450 ms in males or 470 ms in females, or any other relevant ECG finding at screening, or continued use of agents known to prolong the QT interval (refer to listing provided in ISF).
6. Stage 4 kidney disease or requiring dialysis (i.e., eGFR < 30 mL/min/1.73 m²).
7. History of the following cardiac conditions:
 - a) Myocardial infarction within 3 months prior to the first dose

¹ A woman is considered of childbearing potential (WOCBP), i.e. fertile, following menarche and until becoming post-menopausal unless permanently sterile.

Permanent sterilisation methods include hysterectomy, bilateral salpingectomy and bilateral oophorectomy.

Tubal ligation is NOT a method of permanent sterilisation.

A postmenopausal state is defined as no menses for 2 years without an alternative medical cause.

Proprietary confidential information © 2021 Boehringer Ingelheim International GmbH or one or more of its affiliated companies

- b) Unstable angina
- c) Clinically significant long QT features on electrocardiogram (ECG) or history of familial long QT
- 8. Anticipated transfer/discharge to another hospital or care facility other than their place of residence.
- 9. Not committed to full support or intubation (do not resuscitate/do not intubate wishes)
- 10. Allergy to study medication.
- 11. Relevant end-organ failure or other medical conditions (e.g. active cancer, cardiac, gastrointestinal) which based on investigator judgement would interfere with the conduct of this study.
- 12. Experimental, or off-label usage of medicinal products as specific treatments for COVID-19.
- 13. Currently enrolled in another investigational device or drug trial, or less than 30 days or 5 half-lives (whichever is shorter) since ending another investigational device or drug trial(s), or receiving other investigational treatment(s).
- 14. Women who are pregnant, nursing, or who plan to become pregnant while in the trial.

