5. ASSESSMENTS

5.1 ASSESSMENT OF EFFICACY

5.1.1 Proportion of patients alive and free of mechanical ventilation at Day 29

Patients who are alive and free of mechanical ventilation at Day 29 is defined as those who have not died at Day 29 and those who do not depend on mechanical ventilation for breathing at Day 29.

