## **6.6 HANDLING OF MISSING DATA AND OUTLIERS**

All patients will be followed to collect necessary efficacy and safety information, even if patients discontinue study medication prematurely.

For patients who miss WHO clinical progression scales, imputation will be performed using data from other sources if available, e.g., oxygen use, ventilation use, etc.

For patients who miss start date and/or end date of hospitalisation, ventilator use and oxygen use, data will be imputed based on available information on the eCRF page of WHO Clinical Progression Scales.

Proprietary confidential information © 2021 Boehringer Ingelheim International GmbH or one or more of its affiliated companies

If a patient dies while hospitalised, the number of days of hospitalisation will be imputed until day 29 (i.e. 28 days of hospitalisation). If a patient dies while in ICU, the duration of ICU stay will be imputed until day 29. For patients who die before day 29, WHO progression scale will be imputed as 10 for all remaining visits: in addition, duration of oxygen (or ventilation) use will be imputed until day 29.

For patients who are discharged before day 29, WHO progression scale will be imputed using the last available observation if no additional data is available after discharge.

For patients who discontinue treatment early, if the patient is on oxygen/ventilation before discontinuation, the number of days on oxygen/ventilation will be imputed until day 29. If the patient is not on mechanical ventilator at the last observed assessment, the number of ventilator free days will be imputed until day 29.

For missing or incomplete AE dates, BI internal procedures and guidelines will be followed Q2J1. The same philosophy will be applied to missing concomitant medication dates (where applicable), and dates of study medication discontinuation, and trial completion date.

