#### **7.5.2 (Other) Secondary endpoints**

Secondary endpoints will be analyzed on the FAS using treatment policy estimand.

Proprietary confidential information © 2021 Boehringer Ingelheim International GmbH or one or more of its affiliated companies

- Analysis of patients alive and discharged free of oxygen at Day 29 will be conducted using the same model as for the primary endpoint, to assess the difference in proportions of patients with BI 764198 and placebo.
- Analysis of patients with occurrence of any component of composite: In-hospital mortality or intensive care unit (ICU) admission or mechanical ventilation at Day 29, will be conducted using the same model used as the primary endpoint, to assess the difference in proportions of patients with BI 764198 and placebo.
- Time to response, defined as clinical improvement of at least 2 points (from randomisation) on the World Health Organization Clinical Progression Scale, discharge from the hospital, or considered fit for discharge (a score of 0, 1, 2, or 3 on the Clinical Progression Scale), whichever comes first, by Day 29, will be analysed using the Cox proportional-hazards model adjusting for treatment, age, creatinine at baseline, and duration of symptoms before hospitalisation. Hazard ratio and Kaplan-Meier curves with 95% confidence interval will be provided. Patients who do not respond will be censored at Day 29. Patients who prematurely discontinued from the treatment or lost to follow-up will be censored at the time of their last observed assessment. Patients who die prior to observing response will be censored at Day 29.
- The number of ventilator free days will be analysed using an ANCOVA model including treatment, age, creatinine at baseline, and duration of symptoms before hospitalisation. WHO progression scale below 7 are defined as ventilator free. Hence, ventilator free days can be counted as number of days with WHO progression scale below 7 from the day of randomization to day 29. A sensitivity analysis excluding patients who died during treatment period will be conducted.
- Analysis of mortality at Day 15, 29, 60 and 90 will be conducted using the same model as for the primary endpoint, to assess the difference in proportions of patients with BI 764198 and placebo.

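### Ventilator-free days credit unventilated days before death, the deaths-excluded check does not test what follows from this, and one imputation rule conflicts with the death rule

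*SAP*

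**What the plan says.** The protocol lists the number of ventilator-free days by Day 29 as a secondary endpoint (2.1.3) and does not say how deaths are scored. SAP 7.5.2 treats a WHO score below 7 as ventilator free and states that "ventilator free days can be counted as number of days with WHO progression scale below 7 from the day of randomization to day 29". The analysis is an ANCOVA with treatment, age, baseline creatinine and symptom duration.

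Three further rules bear on deaths:

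- SAP 6.6: "For patients who die before day 29, WHO progression scale will be imputed as 10 for all remaining visits".
- SAP 6.6, for early treatment discontinuers: if the patient "is not on mechanical ventilator at the last observed assessment, the number of ventilator free days will be imputed until day 29". No exception is made for a patient who then dies.
- SAP 7.5.2: "A sensitivity analysis excluding patients who died during treatment period will be conducted". This is the only sensitivity analysis for the endpoint.

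Other outcomes penalise death in full. Success on the primary endpoint "is defined as those who have not died at Day 29 and those who do not depend on mechanical ventilation" (Protocol 5.1.1), so any death by Day 29 is a failure. For time to response, "Patients who die prior to observing response will be censored at Day 29" (SAP 7.5.2), which keeps a death as a non-response throughout. A patient who dies in hospital is given the full 28 hospital days (Protocol 7.3, SAP 6.6).

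**The concern.** Every patient enters at score 5 or 6, so nearly every patient who dies has some counted days. The score of 10 removes only the days from death onward. A late death can therefore score better than a long ventilation that the patient survives, and part of a mortality benefit does not reach the mean difference.

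The planned check cannot show how much this matters. Dropping deaths compares survivors only. If the drug saves patients who then spend time on a ventilator, they join the active arm's survivors and lower its mean, while their placebo counterparts are left out as deaths.

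Separately, the Day 29 imputation for early discontinuers and the score of 10 can give two different counts for the same patient. The SAP does not say which prevails.

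**Working it through.** The readable text gives no mortality rate, ventilation duration, SD or expected effect for this endpoint, so there is no plan figure to reproduce. All rates and durations below are assumptions. From the documents come the counting rules, the 29-day window and 65 patients per arm.

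**1. The rules applied day by day**

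- Intubated on Day 15, dies on Day 25: Days 1 to 14 count, giving 14.
- Ventilated on Days 3 to 24, survives: Days 1 to 2 and 25 to 29 count, giving 2 + 5 = 7.
- Stops drug on Day 5, dies unventilated on Day 10: the score-10 rule counts Days 1 to 9, giving 9; the imputation for discontinuers runs to Day 29, giving 29.

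**2. Loss relative to scoring deaths as 0**

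Suppose the drug acts only by preventing some deaths. Let dm be the mortality reduction, d the mean free days of patients who die, and s the mean free days of those saved.

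- SAP rule: dm × (s − d)
- Deaths as 0: dm × s
- Loss: dm × d

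For mortality 20% to 10%, dm = 0.10. The loss is 0.10 × 3 = 0.3 days at d = 3, 0.9 at d = 9 and 0.10 × 15 = 1.5 at d = 15. For 10% to 5% with d = 9 it is 0.05 × 9 = 0.45.

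**3. Deaths excluded**

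Let V0 be the mean free days of the other survivors and mA the active-arm mortality. The expected difference is dm / (1 − mA) × (s − V0). This takes all deaths by Day 29 as excluded, although the SAP wording covers only the treatment period.

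Assume that 10% of patients are ventilated survivors with a mean of 15 free days, and that 70% are never ventilated and score 29. Then V0 = (0.10 × 15 + 0.70 × 29) / 0.80 = 27.25. With s = 15 the result is (0.10 / 0.90) × (15 − 27.25) = −1.36.

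Expected difference in days for mortality 20% to 10%, d = 9:

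| Patients saved by the drug | s | SAP rule | Deaths as 0 | Deaths excluded |
|---|---|---|---|---|
| like other ventilated survivors | 15 | +0.6 | +1.5 | −1.4 |
| half never ventilated | 22 | +1.3 | +2.2 | −0.6 |
| never ventilated | 29 | +2.0 | +2.9 | +0.2 |
| like those who die (extreme) | 9 | 0.0 | +0.9 | −2.0 |

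**4. Sampling variation**

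Simulation: 65 per arm, no covariates, 20,000 trials. Free days are uniform on 3 to 15 for deaths and on 8 to 22 for ventilated survivors. The SE of the difference is 1.4 to 1.5 days under the SAP rule and about 1.9 with deaths as 0. In the first row of the table, the deaths-excluded estimate is below 0 in 90% of trials.

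**5. A drug that reduces ventilation but not death**

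Mortality is 20% in both arms, and ventilated survivors fall from 20% to 10%. The expected difference is 0.10 × (29 − 15) = 1.4 days under both rules. The SE is about 1.5 under the SAP rule and 2.0 to 2.1 with deaths as 0, so mean divided by SE is about 0.9 against 0.7. Here the planned count is the stronger analysis.

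**The case against.** The strongest reply is that the SAP does have a death rule. Score 10 after death, with a count of days below 7, defines days alive and unventilated, which is a coherent quantity. The loss in step 2 exists only relative to a death-as-0 score that neither document mentions. This stands: a reader might infer that deaths have no rule at all, and the text of SAP 6.6 does not support that.

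A reader might also infer that death as 0 is simply better and should replace the planned count. That does not follow. It has the larger mean-to-SE ratio when the drug works by preventing death (step 3), but the order reverses when the drug mainly prevents ventilation (step 5). The trial objective covers both the risk and the severity of ARDS.

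The conflict over discontinuers should seldom arise. Exclusion criterion 9 removes patients "Not committed to full support or intubation", so deaths without ventilation should be few. For discontinuers still in hospital, Flow Chart footnote f asks sites to "collect ventilation and oxygen parameters daily up to Day 29". The score-10 rule is also the more natural reading. All this stands, but the precedence is not written, and 29 is the highest possible count.

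Finally, the primary endpoint counts death as failure, mortality is analysed at Days 15, 29, 60 and 90, and no formal testing is planned (Protocol 7.1). That keeps the point minor. It does not make the deaths-excluded analysis a valid check.

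**Conclusion.** The point holds as a minor one, in three parts. The planned count lets a patient who dies outscore a ventilated survivor. The only planned check conditions on survival and can point against a life-saving drug. Two rules in SAP 6.6 conflict for discontinuers who die.

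Relative to deaths as 0, the reduction is 0.3 to 1.5 days for an assumed mortality fall from 20% to 10% with an assumed 3 to 15 unventilated days before death. A single figure such as 0.9 days needs the further assumption of 9 such days. The reduction is partial: the mean difference reaches zero only in the extreme case where saved patients have as few free days as those who die. A reader might infer that the endpoint misses a mortality benefit altogether; the rules do not support that, because days after death already count as not free. How often the rule conflict would occur cannot be calculated from the documents. The primary and mortality analyses are unaffected.

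**What to change.** 1. SAP 6.6: state that the imputation of ventilator-free days to Day 29 for early discontinuers does not apply to patients who die by Day 29, and that score 10 takes precedence.
2. SAP 7.5.2: name the planned count as days alive and unventilated to Day 29. Add a sensitivity analysis with the same ANCOVA in which any patient who dies on or before Day 29 scores 0.
3. SAP 7.5.2: label the analysis excluding deaths as descriptive only.

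The cost is a few sentences, one derivation rule and one more analysis, with no new data. The added analysis has a larger SE (about 1.9 to 2.1 days against 1.4 to 1.5 in the assumed scenarios) and is the weaker one if the drug mainly reduces ventilation. It should therefore sit beside the planned count and not replace it.

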6.2.2 Treatment period(s)

The treatment period starts with Visit 2 (Day 1, randomization) and ends with the EOT visit (possible Day 2 through Day 29). Patients will remain hospitalised during the treatment period and daily protocol visits will be conducted to complete procedures according the [Flow Chart](#). Patients may receive treatment with study drug for up to 28 days, however if a patient is well enough to be discharged, then study drug may be stopped before the maximum treatment duration (i.e. 28 days).

EOT visit should be completed the day after the last dose of study drug is administered for all patients regardless of discharge status. EOT visit is expected to align with day of discharge, unless it is planned for a patient to remain hospitalised after treatment with study drug is stopped. EOT visit should occur no later than Day 29.

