7.2 PLANNED ANALYSES

7.2.1 General considerations

The efficacy analysis will be performed in all randomized patients who documented to have received at least one dose of trial medication. This set will be called Full Analysis Set (FAS).

Patients will be analysed as randomised, without regard to any treatment changes. The intent-to-treat (ITT) principle will be applied to the randomized set including all observed data in the primary analysis regardless of treatment discontinuation. Baseline refers to the last measurement prior to randomisation.

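### The one sensitivity analysis specified for ventilator-free days drops patients who died on treatment, so it compares non-randomised survivors and cannot test how far the main result depends on the handling of deaths

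*SAP*

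**What the plan says.** SAP 7.5.2 states that "The number of ventilator free days will be analysed using an ANCOVA model", with treatment, age, baseline creatinine and duration of symptoms before hospitalisation in the model. On the count itself it says that "ventilator free days can be counted as number of days with WHO progression scale below 7 from the day of randomization to day 29". The section opens with the general rule: "Secondary endpoints will be analyzed on the FAS using treatment policy estimand".

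Deaths stay in this main analysis. SAP 6.6 says: "For patients who die before day 29, WHO progression scale will be imputed as 10 for all remaining visits". Days after death are therefore not ventilator free, while days before death with a score below 7 still count.

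One further analysis of VFD follows in SAP 7.5.2: "A sensitivity analysis excluding patients who died during treatment period will be conducted".

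The section does not define the treatment period. Protocol 6.2.2 runs it from Visit 2 to the end-of-treatment (EOT) visit, which can fall on any day from Day 2 to Day 29, and adds that "if a patient is well enough to be discharged, then study drug may be stopped before the maximum treatment duration". In SAP Table 6.1: 1 the stop date of the on-treatment period is missing from the public text. So is the interval after last intake in SAP 7.8.1.

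**The concern.** A sensitivity analysis of VFD should show whether the result depends on how deaths are scored. Removing the deaths does something else: it selects patients on an outcome that treatment may affect. Protocol 1.4.1 expects the drug to improve mortality, and mortality is itself a secondary endpoint.

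Suppose that a patient who would have died on placebo survives on the drug after a long spell of ventilation. That patient stays in the drug arm with few VFD, while the counterpart on placebo is deleted. The drug arm then looks worse because it saved someone. For a drug that causes deaths, the same selection works in its favour.

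If this table disagrees with the main ANCOVA, a reader cannot tell selection from fragility of the main result. Protocol 4.1.5.1 says that the unblinded snapshot will guide further development, so a spurious signal in either direction could matter.

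**Working it through.** The plan gives no VFD mean, SD or effect, so there is no figure of its own to reproduce. It also gives no mortality assumption in the public text. The only mortality figure is 25% to 60% for severe ARDS, in Protocol 1.1, and that is background. All inputs below except the counting rules are therefore assumptions.

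**Set-up**
- Mortality is mp on placebo and mt on drug, and the drug kills nobody who would have lived on placebo. The saved share is s = mp - mt.
- Other survivors have mean VFD V on placebo and V + e on drug.
- Saved patients have mean v on drug.
- Patients who die have d VFD before death, the same in both arms.
- All deaths fall inside the exclusion window.

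**Formulas, drug minus placebo**
- Deaths excluded: [(1 - mp)(V + e) + s·v]/(1 - mt) - V
- All patients, death scored 0: (1 - mp)·e + s·v
- All patients, SAP 6.6 rule (VFD before death credited): (1 - mp)·e + s·(v - d)

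**Illustration: mp = 20%, mt = 10%, V = 27, e = 0.** With deaths excluded the difference is (80 × 27 + 10·v)/90 - 27 = (v - 27)/9. With death = 0 it is 0.1·v. Under the SAP rule it is 0.1·(v - d), shown here with d = 6.

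| v (VFD in saved patients) | Deaths excluded | Death = 0 | SAP main rule, d = 6 |
|---|---|---|---|
| 5 | -2.4 | +0.5 | -0.1 |
| 7 | -2.2 | +0.7 | +0.1 |
| 10 | -1.9 | +1.0 | +0.4 |
| 20 | -0.8 | +2.0 | +1.4 |
| 27 | 0 | +2.7 | +2.1 |

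In the mirror case (10% mortality on placebo, 20% on drug, v = 7 on placebo for those whom the drug kills), the deaths-excluded difference is 27 - (80 × 27 + 10 × 7)/90 = +2.2 days in favour of the drug.

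**Second set: 25% v 15%, V = 26, e = 0.** Deaths excluded gives -2.47, -2.12, -1.29 and -0.71 days for v = 5, 8, 15 and 20. For v = 8, death = 0 gives +0.80 and the SAP main rule with d = 6 gives +0.20.

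**When the sign does not reverse.** The deaths-excluded difference is negative only if e < s·(V - v)/(1 - mp). In the second set the break-even gain is 0.10 × 18/0.75 = 2.4 days at v = 8 and 0.10 × 6/0.75 = 0.8 days at v = 20. The scale limits how much gain is possible: the count tops out at 28 or 29 days, depending on whether both end days count.

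**Sampling variation at 65 per arm.** A simulation of 10,000 trials used the second set with v = 8 and e = 0. VFD were normal, clipped to 0-29, with SDs of 6, 5 and 4 for other survivors, saved patients and deaths. A Welch test stood in for the ANCOVA. The deaths-excluded estimate favoured placebo in 96% of trials and was nominally significant for harm in 40%. For the SAP main rule, nominal harm appeared in 2%. With v = 20 the deaths-excluded figures fall to 74% and 9%.

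**Whether the main analysis covers the gap.** It does not rank death as worst. Under SAP 6.6 and 7.5.2, a never-ventilated patient who dies on Day 20 has 19 VFD (Days 1-19). A survivor ventilated on Days 3-24 has 7 (Days 1-2 and 25-29). The table shows the effect on means: with v = 7 the main difference is 0.7 - 0.1·d, which is zero at d = 7 and negative above that.

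**The case against.** The strongest reply is that little hangs on this table. It is a supplementary look at a secondary endpoint that is not key, in a trial that Protocol 7.1 calls exploratory and without formal testing. The main ANCOVA keeps deaths, mortality is analysed at four time points, and the primary endpoint counts death as failure. A drug that halved mortality would be expected to show it there. This stands, and it limits the stakes.

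The second reply is that the size comes from chosen inputs. Nothing in the documents says that saved patients are mostly ventilated survivors. Exclusion criterion 9 removes patients not committed to intubation, which makes that plausible. But the trial aims to reduce the risk or severity of ARDS, so some saved patients may never be ventilated. At v = 27 the bias vanishes, and a VFD gain in the other survivors can offset it. This also stands: a reversal is possible, not certain.

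Third, a reader might infer that the exclusion contradicts Protocol 7.2.1: "Patients will be analysed as randomised, without regard to any treatment changes". It does not. That sentence concerns treatment assignment and treatment changes, and dropping deaths reassigns nobody. A sensitivity analysis may also depart from the treatment-policy rule in SAP 7.5.2. The fair statement is that this one answers a different question from the main analysis.

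Fourth, SAP Table 6.3: 1 allows efficacy sensitivity analyses on the randomised set and, optionally, the per-protocol set. Neither is tied to VFD or deals with death, and parts of the SAP are not public. The statement that this is the one VFD sensitivity analysis applies to the visible text.

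**Conclusion.** The point holds in limited form. The planned exclusion conditions on a post-randomisation outcome, breaks the randomised comparison and does not test the robustness of the main FAS result. Under the assumed inputs the bias runs from 0 to about -2.5 days against a drug that cuts mortality by 10 percentage points. It depends mainly on the VFD of saved patients and on any gain in other survivors.

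Two stronger readings are tempting. One is that the trial would present a life-saving drug as harmful. The documents do not support that, because the main VFD analysis, the mortality analyses and the primary endpoint all keep deaths. The other is that the rule certainly treats deaths before Day 29 unevenly, dropping those on drug and keeping those after the last dose. The window does appear patient-specific under Protocol 6.2.2. But Protocol 7 also speaks of an anticipated four-week treatment period, and part of the SAP definition is missing from the public text. How many later deaths would stay in cannot be settled. What can be said is that this analysis needs its window defined.

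The change is still worth making, because the main analysis credits VFD before death and so no visible VFD analysis treats death as the worst outcome.

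**What to change.** In SAP 7.5.2, replace the exclusion as the VFD sensitivity analysis with one on all FAS patients in which death by Day 29 ranks below every survivor and survivors rank by VFD. A van Elteren test stratified by baseline severity grade would do, as would a proportional-odds model with the primary covariates. The latter gives an estimate with a confidence interval, which suits a trial without formal testing.

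If VFD in survivors is still wanted, define the group by death by Day 29 rather than by the treatment period. Show it descriptively beside mortality, and do not label it a sensitivity analysis.

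The cost is one SAP sentence and one extra table from data already collected. The rank analysis gives no difference in days, but the main ANCOVA still does.
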